4.4 WITHDRAWAL CRITERIA

Grade IV or higher surgical complication (Modified Clavien classification).
Patient choice for any reason.

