
1.2 RATIONALE FOR CURRENT STUDY

From a clinical perspective, national and international guidelines for bariatric surgery have historically been based predominantly on weight. However, bariatric surgery is also highly successful in achieving remission of co-morbidities such as T2DM. The chance of remission does not appear to be weight dependent. In a recent meta-analysis T2DM remission was 72% in patients with a BMI < 35 kg/m² and 71% in patients with a BMI > 35 kg/m² undergoing bariatric surgery¹². Consequently, the latest guidelines by NICE in the UK have been updated to reflect the convincing body of evidence that surgery is also a highly successful and cost-effective treatment for T2DM patients who are less obese. As many as 2 million patients may be eligible for bariatric surgery under these new guidelines. However, unfortunately up to 30% of T2DM patients who undergo bariatric surgery do not achieve remission of their T2DM. There is currently no reliable method of identifying these patients preoperatively. T2DM remission does not appear to correlate with preoperative BMI or any other known clinical or biochemical marker reliably. Therefore novel preoperative biomarkers to help guide clinicians and policy makers select the ideal surgical candidates are urgently required to enable truly personalised healthcare.

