2. STUDY OBJECTIVES

We hypothesise that weight loss and the metabolic effects of bariatric surgery are achieved in part through a functional modification of the gut microbiome and altered microbiome – host metabolome interactions. We aim to elucidate these and other mechanisms of T2DM remission following bariatric surgery. We will explore both the weight dependent and weight independent mechanisms with the translational objectives of 1) identifying novel, surgical and non-surgical, therapeutic targets and 2) identifying novel biomarkers for preoperative prognostication of T2DM remission.

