3.1 STUDY OUTCOME MEASURES

The 1^o clinical outcome measure will be diabetes remission defined as HbA1c < 42 mmol/mol. The 2^o clinical outcomes will be partial diabetes remission (HbA1c < 48 mmol/mol), HbA1c reduction and % excess weight loss.

These clinical outcomes will be mapped to metabolomic and metagenomic data to identify preoperative markers of diabetes remission and weight loss.

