4.3 EXCLUSION CRITERIA

Previous bariatric surgery, previous major abdominal surgery*, pregnancy or intention to become pregnant during trial period, lack of capacity to consent.

* = Small or large bowel resection, liver, pancreatic or splenic surgery, as these will influence the bacteria in the gut and / or the patient's metabolic state, which we are studying. It will not include patients that have previously had an appendicectomy, cholecystectomy, hernia repairs or surgery on other organs not listed above.

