6. ASSESSMENT AND FOLLOW-UP

Patients will undergo follow up according to the usual bariatric surgery follow up protocol at the Imperial Weight Centre.

- At patients usual preoperative, 3 month, 1 and 2 year postoperative outpatient appointments patients will provide additional samples of blood, urine and faeces for analysis.
- Patients will be given brief online 24-hour diet recall questionnaires to complete while waiting for their usual outpatient appointments. They will then be asked to complete entries for two days following each hospital visit using a personal computer via a personal link to a secure website provided.
- Patients will be sent home with 24-hour urine collection bottles. They will be asked to provide 24-hour collections for before surgery and the days before their 3-month and 1-year outpatient visits. They will be able to return their samples when they attend these appointments.
- At the time of surgery researchers will collect resected stomach tissue from LSG patients that would usually be disposed.
- Clinical data will be retrieved from the medical notes preoperatively to 2 years postoperatively.

Study End: 130 type 2 diabetic and 65 non-diabetic patients will be recruited and followed-up until 2 years postoperatively.

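### Does the unexplained withdrawal of patients after a Grade IV or higher complication undermine the preoperative-marker analysis?

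*Combined protocol and SAP*

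**What the plan says.** Section 4.4 of the combined protocol and SAP has two entries: "Grade IV or higher surgical complication (Modified Clavien classification" and the patient's own choice. It does not define what a patient is withdrawn from.

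Three other parts bear on the point, and none settles it.

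- **Section 6** states that "Clinical data will be retrieved from the medical notes preoperatively to 2 years postoperatively". Its study-end statement is that "130 type 2 diabetic and 65 non-diabetic patients will be recruited and followed-up until 2 years postoperatively". Neither mentions withdrawn patients.
- **Section 7** allows for 20% dropout at 1 year, without saying whether complication-related withdrawals are included. It defines no analysis set.
- **Section 8.2** says participants may leave the protocol treatment at any time. It covers participant choice only.

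The aims are mixed. Section 2 includes "identifying novel biomarkers for preoperative prognostication of T2DM remission" but also says "We aim to elucidate these and other mechanisms of T2DM remission following bariatric surgery". Section 3.1 plans to "identify preoperative markers of diabetes remission and weight loss".

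**The concern.** The predictor is sampled before surgery and the complication happens after it. Section 1.2 wants "novel preoperative biomarkers to help guide clinicians and policy makers select the ideal surgical candidates". Nobody making that choice knows who will later have a severe complication. If withdrawal meant removal from the analysis, the marker would be assessed only in patients who turn out to be free of one, which is selection on a post-baseline event. If severe complications were related both to the marker and to failure of remission, the estimated association would be distorted.

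There is also an apparent clash with section 6, which describes follow-up of all recruited patients to 2 years with no exception. Two analysts working from the same text could arrive at different analysis sets.

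**Working it through.** **1. What the text supports.** Section 4.4 allows at least three readings:

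- (a) Research sampling stops, while notes retrieval and analysis continue.
- (b) Follow-up stops, but data already collected are analysed, for example a preoperative sample with an HbA1c recorded before withdrawal.
- (c) The patient leaves both follow-up and analysis.

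Only (c) restricts the marker analysis by rule to patients without the complication, and the section does not state it. Under (b) some patients may lack a later outcome, which is ordinary missing data.

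The section 6 sentence on 130 and 65 patients defines when the study ends. Taken as a promise that nobody leaves, it would also contradict patient-choice withdrawal in sections 4.4 and 8.2 and the dropout allowance in section 7. It is better read as a general statement limited by the specific rules, so there is a lack of clarity but no contradiction.

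**2. The plan's own counts (section 7).** Inputs are 65 diabetic patients per surgical group, 20% dropout and 30% non-resolution.

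- Evaluable: 65 × (1 − 0.20) = 52
- Non-resolution: 52 × 0.30 = 15.6
- Resolution: 52 × 0.70 = 36.4

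Rounded down, these are the stated 15 and 36.

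**3. How many patients are affected.** The complication rate c is an assumption, because the documents give none.

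- 130 × 0.01 = 1.3 and 130 × 0.04 = 5.2 diabetic patients
- Expected dropouts: 130 × 0.20 = 26
- Share of that allowance: 1.3/26 = 5% to 5.2/26 = 20%

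**4. Effect on the smaller group.** If these patients are already within the 20%, or stay in follow-up, the count stays at 15.6. If they are lost on top of it and resolve at the average rate:

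| c | Added to the 20%: 65 × (0.80 − c) × 0.30 | Applied after the 20%: 15.6 × (1 − c) |
|---|---|---|
| 1% | 15.4 | 15.4 |
| 2% | 15.2 | 15.3 |
| 3% | 15.0 | 15.1 |
| 4% | 14.8 | 15.0 |

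The expected count falls below 15 at c = 0.80 − 15/(0.30 × 65) = 3.1% on the first formula, and at c = 1 − 15/15.6 = 3.8% on the second. The largest loss in the table is 15.6 − 14.8 = 0.8 of a patient. The chance variation in that count, with 52 evaluable patients, has standard deviation √(52 × 0.30 × 0.70) = 3.3.

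**5. Effect on a marker under reading (c).** One normally distributed marker stands in for the multivariate model. Assumptions:

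- 30% non-remitters
- true AUC 0.70 or 0.80, with mean difference √2 × z(AUC)
- logistic withdrawal with mean rate 1% or 4%
- odds ratios 0.5, 1 or 2 per marker standard deviation, and 0.5, 1 or 2 for non-remission

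The AUC was recomputed in the patients retained.

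| c | Range of AUC shift |
|---|---|
| 1% | −0.0017 to +0.0007 |
| 4% | −0.0064 to +0.0027 |

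The shift is zero when withdrawal is unrelated to the marker. The extreme, −0.0064, needs the 4% rate, both odds ratios equal to 2 and a true AUC of 0.70.

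The Hanley-McNeil standard errors are:

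| Non-remitters v remitters | AUC 0.70 | AUC 0.80 |
|---|---|---|
| 15.6 v 36.4 (one surgical group) | 0.084 | 0.073 |
| 31.2 v 72.8 (both groups) | 0.059 | 0.052 |

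The worst shift is 0.0064/0.084 = 8% of one standard error in a single surgical group, and 0.0064/0.059 = 11% with both groups pooled.

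**The case for a change.** The best case for a change is that the scope of withdrawal should be fixed before outcomes are seen, whatever the size of the effect. Selection on an event after baseline is a recognised weakness in prognostic work, one sentence in section 4.4 would remove the doubt, and notes retrieval is already planned, so no visits would be added. The margin over 15 non-remitters is also only 0.6 of a patient, while section 7 asks for more than 15 per group.

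Part of this stands. The ambiguity is real, and no part of the text available for review resolves it. If patients were excluded on this ground, the report should say that the marker result is conditional on a postoperative event.

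The rest carries less weight. The harm depends on an exclusion rule that the plan does not state. The thin margin comes from the sample-size inputs and is swamped by chance variation in the count. A reason for setting such patients aside in mechanistic work is also conceivable. Section 4.3 excludes certain earlier operations "as these will influence the bacteria in the gut and / or the patient's metabolic state, which we are studying", and a severe complication could be viewed in the same way. That reason is weaker for the prognostic aim. Finally, retention of data after withdrawal is a usual subject of consent and information sheets, which were not available for review, so it cannot be called missing.

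**Conclusion.** The concern identifies a gap in wording, and no change to the plan follows. Section 4.4 leaves the scope of withdrawal open, but it does not contradict section 6 and does not direct exclusion from analysis. An analyst would ordinarily keep the preoperative sample and whatever outcome data consent allows, and would report how many patients were withdrawn for this reason. A separate sensitivity analysis on about 1 to 5 diabetic patients could show almost nothing.

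Under the least favourable reading, the AUC shift is at most 0.0064 against a standard error of 0.084 for one surgical group, and the expected number of non-remitters falls by less than one per group. If these patients fall within the 20% allowance, the planned counts do not change.

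This rests on an assumed complication rate of 1% to 4%, withdrawal odds ratios between 0.5 and 2, and a single marker in place of the planned multivariate models, so the figures are illustrative. A much higher rate would matter more: at 10% added to the dropout, expected non-remitters would be 65 × 0.70 × 0.30 = 13.7 per group. No view is taken on whether the withdrawal criterion itself is right.

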5. ADVERSE EVENTS

As no added clinical interventions / procedures will occur in this study NO adverse events are expected as a result of participating.

5.1 DEFINITIONS

Adverse Event (AE): any untoward medical occurrence in a patient or clinical study subject.

Serious Adverse Event (SAE): any untoward and unexpected medical occurrence or effect that:

- **Results in death**
- **Is life-threatening** – *refers to an event in which the subject was at risk of death at the time of the event; it does not refer to an event which hypothetically might have caused death if it were more severe*
- **Requires hospitalisation, or prolongation of existing inpatients' hospitalisation**
- **Results in persistent or significant disability or incapacity**
- **Is a congenital anomaly or birth defect**

Medical judgement should be exercised in deciding whether an AE is serious in other situations. Important AEs that are not immediately life-threatening or do not result in death or hospitalisation but may jeopardise the subject or may require intervention to prevent one of the other outcomes listed in the definition above, should also be considered serious.

5.3 REPORTING PROCEDURES

All adverse events should be reported. Depending on the nature of the event the reporting procedures below should be followed. Any questions concerning adverse event reporting should be directed to the Chief Investigator in the first instance.

5.3.1 Non serious AEs

All such events, whether expected or not, should be recorded.

5.3.2 Serious AEs

An SAE form should be completed and faxed to the Chief Investigator within 24 hours. However, hospitalisations for elective treatment of a pre-existing condition do not need reporting as SAEs.

All SAEs should be reported to the East of Scotland Research Ethics Service where in the opinion of the Chief Investigator, the event was:

- 'related', ie resulted from the administration of any of the research procedures; and
- 'unexpected', ie an event that is not listed in the protocol as an expected occurrence

Reports of related and unexpected SAEs should be submitted within 15 days of the Chief Investigator becoming aware of the event, using the NRES SAE form for non-IMP studies. The Chief Investigator must also notify the Sponsor of all SAEs.

Local investigators should report any SAEs as required by their Local Research Ethics Committee, Sponsor and/or Research & Development Office.

Contact details for reporting SAEs

Email: [contact]

**Please send SAE forms to: Tayside medical Science Centre [name],
[name], Ninewells Hospital and Medical School [name]**

[contact] (Mon to Fri 09.00 – 17.00)

6. ASSESSMENT AND FOLLOW-UP

Patients will undergo follow up according to the usual bariatric surgery follow up protocol at the Imperial Weight Centre.

- At patients usual preoperative, 3 month, 1 and 2 year postoperative outpatient appointments patients will provide additional samples of blood, urine and faeces for analysis.
- Patients will be given brief online 24-hour diet recall questionnaires to complete while waiting for their usual outpatient appointments. They will then be asked to complete entries for two days following each hospital visit using a personal computer via a personal link to a secure website provided.
- Patients will be sent home with 24-hour urine collection bottles. They will be asked to provide 24-hour collections for before surgery and the days before their 3-month and 1-year outpatient visits. They will be able to return their samples when they attend these appointments.
- At the time of surgery researchers will collect resected stomach tissue from LSG patients that would usually be disposed.
- Clinical data will be retrieved from the medical notes preoperatively to 2 years postoperatively.

Study End: 130 type 2 diabetic and 65 non-diabetic patients will be recruited and followed-up until 2 years postoperatively.

7. STATISTICS AND DATA ANALYSIS

Multivariate statistical analysis will be performed on the generated metabonomic and metagenomic data sets. This will include unsupervised principal components analysis (PCA) and supervised partial least squares discriminant analysis with orthogonal signal correction (OPLS-DA) and O2-PLS between data sets. Mapping T2DM outcomes to metabonomic and metagenomic data will potentially identify novel preoperative biomarkers that are able to prognosticate T2DM resolution following bariatric surgery.

Due to the complexity of metabonomic data sample size calculations are difficult and there is currently no standardised technique. We used peer-reviewed MetSizeR methodology to calculate appropriate sample sizes¹³. Using principal component analysis on an expected metabonomic data set of 300 metabolites of which 20% differentiate significantly and a targeted false discovery rate of 5%, over 15 samples are needed in each group.

Approximately 30% of obese diabetic patients do not have resolution of disease following bariatric surgery¹². To allow for an expected drop out rate of 20% at 1 year we will recruit 65 patients undergoing RYGB and 65 patients undergoing VSG to achieve 15 patients with non-resolution of diabetes and 36 patients with resolution in each surgical group. We will also aim to recruit 65 non-diabetic patients undergoing surgery to act as a control group. This will enable comparison against diabetic patients that undergo remission after surgery.

Four surgeons at the Imperial Weight Centre collectively perform approximately 220 RYGB and 180 VSG procedures a year. In previous years 25% of patients have had T2DM. However, we expect this percentage to rise since the introduction of new NICE guidelines encouraging bariatric surgery in diabetic patients in November 2014. We expect to recruit 1-2 patients a week that meet the inclusion criteria and have completed recruitment after 18 months.

Data and all appropriate documentation will be stored for a minimum of 10 years after the completion of the study, including the follow-up period.

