4.2 INCLUSION CRITERIA

Referred to the Imperial Weight Centre (NHS) Tier 4 service team for consideration bariatric surgery (RYGB / VSG / mRYGB / LAGB), Obese (BMI>30kg/m²), Age ≥18, failure of efforts at lifestyle modification and dieting, fitness for anaesthesia and procedure, willingness to comply with the trial protocol.

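### Section 7 plans no clinical benchmark for the remission markers, so omics features that only track preoperative HbA1c or other markers of disease stage can be reported as novel

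*Combined protocol and SAP*

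**What the plan says.** - **Purpose.** Section 1.2 justifies the search for new markers by saying that "T2DM remission does not appear to correlate with preoperative BMI or any other known clinical or biochemical marker reliably". The value sought is prediction that clinical data do not already give.
- **Entry.** The inclusion criteria (4.2) cover referral, BMI and age, then "failure of efforts at lifestyle modification and dieting, fitness for anaesthesia and procedure, willingness to comply with the trial protocol". The exclusions (4.3) are "Previous bariatric surgery, previous major abdominal surgery*, pregnancy or intention to become pregnant during trial period, lack of capacity to consent". Neither list mentions HbA1c, diabetes duration or glucose-lowering treatment.
- **Primary outcome.** Section 3.1 gives "diabetes remission defined as HbA1c < 42 mmol/mol", with no reference to the starting value.
- **Analysis.** Section 7 names PCA, then "supervised partial least squares discriminant analysis with orthogonal signal correction (OPLS-DA) and O2-PLS between data sets", and goes straight to the inference: "Mapping T2DM outcomes to metabonomic and metagenomic data will potentially identify novel preoperative biomarkers that are able to prognosticate T2DM resolution following bariatric surgery". It names no clinical covariate, no stratification by stage, no clinical-only model and no test of added value.
- **Clinical data.** Section 6 says "Clinical data will be retrieved from the medical notes preoperatively to 2 years postoperatively". It lists no variables and gives them no role in the biomarker analysis.

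**The concern.** The outcome is the crossing of an absolute HbA1c line, so the starting HbA1c sets how far a patient must fall. As an illustration, a patient who starts at 46 mmol/mol is 46 − 42 = 4 above the line; one who starts at 95 is 95 − 42 = 53 above it. If preoperative HbA1c, or another measure of stage, carries information about remission, then any metabolite or taxon that follows it will also be associated with remission.

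Nothing in the planned methods separates such a feature from a new marker:

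- The orthogonal correction in OPLS-DA removes variation unrelated to the outcome. Stage variation that predicts remission is related to it and stays in.
- False discovery rate control guards against features with no association. A stage proxy has a true association.
- The 65 non-diabetic controls cannot distinguish stages among diabetic patients.

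At stake is the claim that section 1.2 wants to make: better selection of surgical candidates than present clinical data allow.

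**Working it through.** **1. The plan's own figures (section 7).** Recruited per procedure 65, dropout 20%, non-resolution 30%.

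- Evaluable: 65 × (1 − 0.20) = 52.
- Non-remitters: 52 × 0.30 = 15.6 (stated 15). Remitters: 52 × 0.70 = 36.4 (stated 36).
- Both procedures together: 2 × 15 = 30 and 2 × 36 = 72.

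The group sizes reproduce. The requirement of over 15 per group cannot be rebuilt, because no effect sizes or covariances are given.

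**2. Assumptions.** The documents do not give these, so a range is shown.

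- Stage is a normal score S that separates non-remitters from remitters with AUC 0.50 to 0.80. The standardised difference is d = √2 × Φ⁻¹(AUC): 0 at 0.50, 0.36 at 0.60, 0.74 at 0.70, 0.95 at 0.75, 1.19 at 0.80.
- 60 of 300 features equal r × S + √(1 − r²) × noise, with r = 0.3 or 0.5, and have no other link to remission. The other 240 are noise. The count of 60 borrows the 20% in the sample-size paragraph, which refers to features that differ between groups, not to features that track stage.
- A feature is declared by t-test with Benjamini-Hochberg at 5%. Section 7 uses 5% FDR only for sample size and states no rule for declaring a marker.

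**3. Hand check of one setting.** With AUC 0.70 and r = 0.5, the feature difference is 0.5 × 0.74 = 0.37 SD. For 15 v 36 the standard error is √(1/15 + 1/36) = 0.307, so the expected t is 0.37 / 0.307 = 1.21. Against a critical value of 2.01, a single proxy reaches p < 0.05 with probability about Φ(1.21 − 2.01) = 0.21. Simulation gives 0.22.

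**4. Chance that at least one stage-only feature is declared, r = 0.5.** Ranges are across repeated simulation runs of 400 to 3,000 replicates; with 400, the standard error near 50% is √(0.5 × 0.5 / 400) = 2.5 points.

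| AUC of stage | 15 v 36 (per procedure) | 30 v 72 (pooled) |
|---|---|---|
| 0.50 | 1–2% | about 1% |
| 0.60 | 2–4% | 7–8% |
| 0.70 | 16–19% | 47–48% |
| 0.75 | 33–36% | 73–77% |
| 0.80 | 57–63% | 94–98% |

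**5. Sensitivity.**

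- r = 0.3, AUC 0.70–0.80: about 5–20% (15 v 36) and 16–59% (30 v 72).
- 10 proxies instead of 60, r = 0.5, AUC 0.70: about 3–4% (15 v 36) and 13–15% (30 v 72).
- After adjustment for S: about 2% or less in every setting, and each proxy reaches p < 0.05 at the nominal 5%.

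**6. Room for a benchmark.** HbA1c, duration, insulin use and one marker make four parameters: 15 / 4 = 3.75 non-remitters per parameter within a procedure, 30 / 4 = 7.5 pooled. With procedure as a fifth term, 30 / 5 = 6. A model must therefore be pooled, small and penalised.

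**The case against.** The best reply is section 1.2 itself: if known clinical markers do not predict remission, there is no stage signal to proxy. At AUC 0.50 that is right, and the table shows no excess. But the sentence says that the markers are not reliable, which is weaker than carrying no information. The only figures given beside it (remission 72% and 71% below and above a BMI of 35 kg/m²) concern BMI, not HbA1c. It is a premise that this cohort can test, and the plan does not test it.

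Several further objections stand. The percentages depend on assumed inputs and on a declaration rule that the plan does not name, so they are not error rates of this plan. The plan is sized per procedure and describes no pooling, so the left column is the relevant one. Diabetes duration and insulin use appear nowhere in the documents; only preoperative HbA1c is tied to the outcome by the text.

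A reader might infer that the study is unable to separate new markers from proxies at all. The documents do not support that. Clinical data are retrieved from the preoperative period onward, and the secondary outcome of HbA1c reduction already requires a preoperative value. The comparison can be made; it is not prespecified.

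A reader might also infer that a stage-linked feature is a false finding. It is not: it may predict remission, and it may matter for the mechanistic and therapeutic-target aims in section 2. The plan's own wording is also cautious, since it says only that the work will "potentially identify novel preoperative biomarkers that are able to prognosticate T2DM resolution following bariatric surgery".

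**Conclusion.** The concern holds in a limited form. The plan has open entry by diabetes stage, an outcome fixed on the HbA1c scale and no clinical comparator. A feature that restates preoperative HbA1c, or another stage measure recorded in the notes, could be reported as a novel prognostic marker. Its ability to predict is not in doubt; the claim of novelty or of value beyond clinical data is unsupported by the analysis as written.

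At the planned per-procedure size, the illustrative risk runs from negligible (1–4% at AUC 0.50–0.60) to more than half (57–63% at 0.80, r = 0.5), and it is lower with weaker correlation or fewer proxies. Which part of that range applies is unknown. The high pooled figures should not be read as a forecast. The uncertainty is itself a reason to plan the benchmark, since without it nobody can tell which case holds. The data stay usable either way, so this is a change that should be made, not a fatal flaw.

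**What to change.** In section 7, prespecify a small, penalised clinical reference model for the primary remission outcome, fitted across both procedures with procedure as a covariate. It should contain preoperative HbA1c and, where the notes record them, diabetes duration and insulin use. Name these items in the notes extraction in section 6.

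Report each candidate feature or omics score with and without adjustment for this model, and give the cross-validated change in AUC over it with an interval. Keep 'novel' and 'adds to clinical data' for markers whose association holds after adjustment, and report the others as correlates of disease stage. Do not make the AUC gain a pass/fail gate: with 15 to 30 non-remitters it is too imprecise, and real markers would fail it.

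The cost is wording, one extra model, and two or three variables taken from the notes. No visits, samples or recruitment are added. The downside is that fewer features will qualify as novel.

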4. PARTICIPANT ENTRY

4.1 PRE-REGISTRATION EVALUATIONS

Potential participants will have their notes screened by NHS team members to identify patients that meet the inclusion / exclusion criteria. They will then be asked if they are happy to talk to the research team to discuss the project and undergo informed consent to take part.

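### Can 18 months at one to two patients a week deliver the recruitment target, and does it matter if it cannot?

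*Combined protocol and SAP*

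**What the plan says.** Section 7 gives the recruitment forecast: "We expect to recruit 1-2 patients a week that meet the inclusion criteria and have completed recruitment after 18 months". The sentences just before it supply the basis. The centre's four surgeons "collectively perform approximately 220 RYGB and 180 VSG procedures a year. In previous years 25% of patients have had T2DM", and "we expect this percentage to rise since the introduction of new NICE guidelines". No size is given for that rise, and no share is given by procedure.

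The diabetic target in the same section is "65 patients undergoing RYGB and 65 patients undergoing VSG to achieve 15 patients with non-resolution of diabetes and 36 patients with resolution"; the last two counts apply per procedure. There are also to be 65 non-diabetic controls. Study End, in Section 6, gives the totals: "130 type 2 diabetic and 65 non-diabetic patients will be recruited", with follow-up to two years after surgery.

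Section 4.2 admits obese adults referred "for consideration bariatric surgery (RYGB / VSG / mRYGB / LAGB") and does not mention diabetes. The Study Summary gives 18 months of recruitment and two years of follow-up. Section 3 gives a total study time, recruitment included, of 60 months.

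**The concern.** Three things look wrong.

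- **Whom the rate covers.** The forecast refers to patients who meet the inclusion criteria, and those criteria admit people without diabetes. Taken at its word, the forecast cannot reach 195 in 18 months.
- **A thin margin.** If the rate is meant for diabetic patients only, the target fits the stated range but uses up most of the diabetic caseload. Exclusions such as "Previous bariatric surgery, previous major abdominal surgery" reduce that supply, and so do refusals. Section 4.1 has two points at which a patient can decline: after notes are screened, "They will then be asked if they are happy to talk to the research team", and consent follows. Section 7 allows for dropout after enrolment but not for losses before it.
- **Unexplained time.** Eighteen months plus two years is 42 months, and the plan states 60 without saying how the rest is used.

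The sample size has little slack. Section 7 wants more than 15 samples in each group and expects about 15 non-resolvers per procedure. If recruitment stopped at 18 months with one procedure short, that procedure's comparison of resolvers with non-resolvers would fall below the plan's own minimum.

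**Working it through.** **Inputs.** From Section 7: 220 RYGB and 180 VSG procedures a year, 25% with T2DM, 65 diabetic patients per procedure, 65 controls, 20% dropout at one year, 30% non-resolution, 1 to 2 patients a week, 18 months (78 weeks). From Section 3: 60 months in total. From Section 6: two years of follow-up. The enrolment fractions and raised T2DM shares used below are my assumptions; the documents give none.

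**The plan's own sample size reproduces.** 65 × 0.8 = 52 evaluable per procedure; 52 × 0.3 = 15.6 non-resolvers and 52 × 0.7 = 36.4 resolvers, matching the stated 15 and 36.

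**Reading 1: the rate covers all participants.**

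- Yield: 78 × 1 = 78 to 78 × 2 = 156.
- Needed: 130 + 65 = 195, or 195 / 78 = 2.5 a week.
- At 2 a week: 195 / 2 = 97.5 weeks = 22.5 months. At 1 a week: 195 weeks = 45 months.

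On this reading the rate and the period do not fit together.

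**Reading 2: the rate covers diabetic patients.**

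- Needed: 130 / 78 = 1.67 a week, in the upper part of the range.
- At 1, 1.5 and 2 a week, 130 patients take 30, 20 and 15 months.
- Diabetic procedures: 400 × 0.25 / 52 = 1.92 a week. This is close to the top of the stated range and supports this reading.
- Controls do not limit recruitment: 400 × 0.75 × 1.5 = 450 non-diabetic procedures, and 65 / 450 = 14%.

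**Share of the diabetic caseload needed in 18 months (Reading 2).** The 25% row uses the historical share. The VSG column assumes the same share in both procedures.

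| T2DM share | Diabetic procedures, all | Needed for 130 | Diabetic VSG | Needed for 65 |
|---|---|---|---|---|
| 25% | 400 × 0.25 × 1.5 = 150 | 87% | 180 × 0.25 × 1.5 = 67.5 | 96% |
| 30% | 180 | 72% | 81 | 80% |
| 35% | 210 | 62% | 94.5 | 69% |

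Without the equal-share assumption, the smaller diabetic group at a 25% overall share is at most 150 / 2 = 75, so at least one procedure needs 65 / 75 = 87% or more.

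**Does an overrun fit the 60 months?** At a 25% share, diabetic VSG procedures arrive at 180 × 0.25 / 12 = 3.75 a month, so 65 take 65 / (3.75 × c) months if a fraction c enrols.

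| Enrolled fraction c | Months to 65 VSG | Plus 24 months of follow-up |
|---|---|---|
| 80% | 21.7 | 45.7 |
| 70% | 24.8 | 48.8 |
| 60% | 28.9 | 52.9 |

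All three are under 60. Leaving 60 − 24 = 36 months (156 weeks) for recruitment, 130 patients need 130 / 156 = 0.83 a week, and all 195 need 195 / 156 = 1.25 a week.

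**The case for a change.** The best case for an edit is that the forecast is unclear on either reading and that one phrase would settle it. The literal reading gives a real mismatch (at most 156 against 195), and the diabetic-only reading is nowhere stated. The margin also bears on the sample size. If recruitment did stop at 18 months with 80% of diabetic VSG patients enrolled at a 25% share, 67.5 × 0.8 = 54 would enter and 54 × 0.8 × 0.3 = 13.0 non-resolvers would be expected, below the 15 the plan wants.

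The ambiguity stands, and so does the observation that the forecast is optimistic. The harm depends on a stop at 18 months that no passage imposes; the plan presents 18 months as an expectation and ends on numbers. The VSG figure of 96% rests on a share by procedure that the documents do not give. The 25% share is a figure for past years that Section 7 expects to rise. Procedures performed in the same 18 months are also an imperfect measure of supply, because patients enter at referral: some are already in the pathway at the start, and some recruited late have surgery afterwards.

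The 60 months is not unlimited. Waits before surgery and laboratory work may draw on it, and on the literal reading a rate of only 1 a week would take 45 + 24 = 69 months. That would be a slow study, to be handled by monitoring accrual; restating the forecast would not enrol anyone sooner.

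The remaining points are editorial. Forty-two months fits inside 60. Section 7's 65 RYGB and 65 VSG patients add up to the 130 in Study End, and the glossary lists mRYGB and LAGB as separate procedures, so a reader can see how the diabetic quota is filled.

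**Conclusion.** No change follows. The sentence is a loosely worded planning forecast, and its context points to diabetic patients. On that reading the stated figures agree: 1.67 a week lies within 1 to 2, and the required 87% of the diabetic caseload is below 100%, as is the assumption-dependent 96% for VSG. What remains is a feasibility risk, which eases to 72% overall if the T2DM share reaches an assumed 30%.

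If recruitment is slow, the study runs longer. For the 60%, 70% and 80% VSG enrolment considered, recruitment plus follow-up takes 46 to 53 months against the stated 60. The outcome definition, the groups compared and the multivariate analysis do not depend on the accrual rate, so results obtained by following the plan would be no less sound.

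This rests on recruitment continuing until the Study End numbers are reached, a steady caseload at the stated volumes, and a T2DM share that does not fall below 25%. At an assumed 20%, only 400 × 0.20 × 1.5 = 120 diabetic procedures would arise in 18 months, and 130 could not be met from them in that time; Section 7 expects movement in the other direction.
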